7.4.	Descriptive Analyses	31

7.5	Primary Aim Analyses	31
7.6	Secondary Aim Analyses	33
7.7	Tertiary Aim Analyses	33
7.8	Mechanisms Analyses	33
8.0	ADMINISTRATIVE CONSIDERATIONS	34
8.1	Conduct of the Trial	34
8.2	Data Management	34
8.3.	Data and Safety Monitoring Plan and Event Reporting	34
9.0	REFERENCES	35

ABSTRACT

This study continues our recently completed "parent" R01 grant ([AA015069](#)). The parent R01 tested a CBT program for alcohol use disorder (AUD) patients with co-occurring anxiety disorders. The program devoted 3 sessions to each of two putative therapeutic mechanisms: 1) anxiety reduction; and, 2) "de-coupling" the cognitive and behavioral bonds linking anxiety to alcohol use (anxiety reduction alcohol outcome expectancies [AR-AOEs], drinking to cope, and conditioned associations). The RCT showed that when added to AUD treatment as usual (TAU), the CBT resulted in significantly better 4-month alcohol outcomes (e.g., 41% relapse) than did TAU plus a stress/anxiety management control group (e.g., 54% relapse) or a non-randomized cohort undergoing TAU alone (e.g., 61% relapse). However, these effects were only small to medium and fell short by about 50% of fully mitigating the deleterious effect on alcohol outcomes conferred by co-occurring anxiety disorders (e.g., Driessen et al., 2001; Kushner et al., 2005).

Using a dismantling design to test these possibilities, we propose to recruit 350 patients to obtain a final sample of 300 cases with baseline and follow-up data who are randomized to one of three study groups: 1) six sessions of CBT for anxiety reduction (CBT-AR); 2) six sessions of CBT for anxiety-alcohol de-coupling (CBT-DC); or, 3) the original CBT from the parent R01 with three sessions devoted to anxiety reduction and to anxiety-alcohol de-coupling each (CBT-O). To enhance feasibility of the renewal work and ensure its continuity/interpretability with the parent R01, the population and procedures of the proposed work are matched to those used in the parent R01. In brief, alcohol dependent individuals with a co-occurring anxiety disorder will be enrolled within one week of beginning the 28-day residential AUD treatment program, "Lodging Plus." Patients will undergo five significant assessments: 1) Baseline Assessment (after being deemed eligible but prior to randomization); 2) Post-Treatment Assessment (immediately following the conclusion of the six-session treatment and prior to being discharged from Lodging Plus); 3) One-Month Assessment (about 30 days following completion of the study treatment); 4) Four-Month Assessment (about 120 days following completion of the study treatment); and, 5) Eight-Month Assessment (240 days following completion of the study treatment). Primary alcohol outcomes measures will include categorical variables (any alcohol use) and percent or count variables (e.g., days drinking, drinks per drinking occasion). We will also measure alcohol dependence and hazardous drinking statuses at

Dismantling the Components and Dosing of CBT for Co-Occurring Disorders

follow-ups as well as obtain information about other anxiety or alcohol treatments obtained following the study treatment.

PROJECT DESIGN

Design Overview

We propose to recruit 350 patients to obtain a final sample of 300 cases with baseline and follow-up data who are randomized to one of three study groups: 1) six sessions of CBT for anxiety reduction (CBT-AR); 2) six sessions of CBT for anxiety-alcohol de-coupling (CBT-DC); or, 3) the original CBT from the parent R01 with three sessions devoted to anxiety reduction and to anxiety-alcohol de-coupling each (CBT-O). To enhance feasibility of the renewal work and ensure its continuity/interpretability with the parent R01, the population and procedures of the proposed work are matched to those used in the parent R01. In brief, alcohol dependent individuals with a co-occurring anxiety disorder will be enrolled within one week of beginning the 28-day residential alcohol use disorder (AUD) treatment program, "Lodging Plus." Patients will undergo five significant assessments: 1) Baseline Assessment (after being deemed eligible but prior to randomization); 2) Post-Treatment Assessment (immediately following the conclusion of the six-session treatment and prior to being discharged from Lodging Plus); 3) One-Month Follow-Up Assessment (30 days following completion of the study treatment); 4) Four-Month Follow-Up Assessment (120 days following completion of the study treatment); and, 5) Eight-Month Follow-Up Assessment (240 days following completion of the study treatment). Primary alcohol outcomes measures will include categorical variables (any alcohol use) and percent or count variables (e.g., days drinking, drinks per drinking occasion). We will also measure alcohol dependence and hazardous drinking statuses at follow-ups. Predictions are based on the parent R01 findings suggesting (but not demonstrating) a dose-dependent positive relationship for de-coupling therapy elements but not anxiety reduction therapy elements in terms of alcohol outcomes; i.e., CBT-DC > CBT-O > CBT-AR on alcohol outcomes. As a means of confirming that the therapeutic mechanisms targeted were responsible for the group differences obtained, process measures of the therapeutic mechanisms are included at all assessments both to verify their dose-dependent activation in groups and to track temporal patterns of change on the mechanisms relative to the outcomes over follow-ups.

Study Aims:

Primary Aim: To test the dismantled CBT effects by comparing the CBT-DC group to the CBT-AR group on alcohol outcomes. We predict that the CBT-DC group will have superior alcohol outcomes compared to the CBT-AR group. This result would confirm that the de-coupling therapy elements are more active in improving alcohol use disorder (AUD) outcomes than are the anxiety reduction therapy elements.

Secondary Aim: To test dose vs. synergy effects of de-coupling therapy by comparing the CBT-DC group to the CBT-O group on alcohol outcomes. We predict that the CBT-DC group will have superior alcohol outcomes compared to the CBT-O group. This result would show the dose-response effects of de-coupling therapy on alcohol outcomes (6 vs. 3 DC sessions) and confirm that the de-coupling therapy effect on alcohol outcomes is not dependent upon its combination (synergy) with anxiety reduction elements. Alternatively, if CBT-O is superior to CBT-DC, then the critical role of synergy would be demonstrated.

Tertiary Aim: To test the dose effects of anxiety reduction therapy by comparing the CBT-AR group to the CBT-O group on alcohol outcomes. We predict that the CBT-O group will have superior alcohol outcomes compared to the CBT-AR group. Assuming synergy was ruled out in the Secondary Aim, this result would further confirm the hypothesized dose-response effects of de-coupling therapy on alcohol outcomes (3 vs. zero DC sessions). Alternatively, if the CBT-AR group is superior to the CBT-O group, then a critical role for the higher dose of anxiety reduction therapy would be demonstrated.

Recruitment Goal and Strategy:

Strategy: We will recruit individuals entering residential treatment for an alcohol use disorder at the Fairview Hospital Chemical Dependency program (Lodging Plus) for adults in Minneapolis. Participants will be recruited from the Consortium of Addiction Research (CAR) combined screening process, approved as IRB protocol #STUDY00005170. Complete details of the screening process can be found in the protocol for that study. Those who are eligible based on the CAR screening protocol will be invited to participate via the “1404S49427 Invite” and given a copy of the consent form. At the Baseline appointment they will have time to read the consent form and have their questions answered. In addition, they will watch a brief video of the study PI describing key elements of the study. If the staff person conducting the screening appointment is convinced the individual understands the consent form based on their answers to questions highlighting the key elements of participation, the individual will be offered the opportunity to sign the consent form. After signing the Consent Form, the baseline appointment will be completed and the appointments for the CBT therapy will be arranged.

Goals: The Lodging Plus program enrolls about 5 to 10 patients per week and our past experience using this recruitment strategy and inclusion/exclusion criteria allows us to recruit about 2 participants per week. This should allow us to achieve the recruitment goal of 350 individuals in a little over 44 months; however, since recruitment can be uneven at times (e.g., slower around major holidays), we have budgeted 48 months to meet the recruitment goal in this 60 month study. Based on our past experience conducting research in this population, this recruitment goal is feasible using the strategy described.

Participant Population:

Participants will meet DSM IV diagnostic criteria for Panic Disorder (PD), Generalized Anxiety Disorder (GAD), and/or Social Anxiety Disorder (SAD) within the past 30 days; receive current inpatient treatment at Lodging Plus primarily for alcohol (vs. other drug) dependence; and have used in the 30 days preceding the study. They will be recruited through the Fairview Hospital Chemical Dependency program (Lodging Plus) for adults in Minneapolis. Study staff will determine competence to consent and obtain written informed consent from all participants before protocol-specified procedures.

Schema or Brief Procedural Steps:

We propose to recruit 350 patients to obtain a final sample of 300 cases with baseline and follow-up data who are randomized to one of three study groups: 1) six sessions of CBT for anxiety reduction (CBT-AR); 2) six sessions of CBT for anxiety-alcohol de-coupling (CBT-DC); or, 3) the original CBT from the parent R01 with three sessions devoted to anxiety reduction and to anxiety-alcohol de-coupling each (CBT-O). To enhance feasibility of the renewal work and ensure its continuity/interpretability

with the parent R01, the population and procedures of the proposed work are matched to those used in the parent R01. In brief, alcohol dependent individuals with a co-occurring anxiety disorder (SAD, GAD or PD/Ag) will be enrolled within one week of beginning the 28-day residential AUD treatment program, "Lodging Plus." Patients will undergo five significant assessments: 1) baseline (after being deemed eligible but prior to randomization); 2) post-treatment (immediately following the conclusion of the six-session treatment and prior to being discharged from Lodging Plus); 3) one-month (30 days following completion of the study treatment); 4) four-months (120 days following completion of the study treatment); and, 5) Eight-months (240 days following completion of the study treatment). Primary alcohol outcomes measures will include categorical variables (any alcohol use) and percent or count variables (e.g., days drinking, drinks per drinking occasion). We will also measure alcohol dependence and hazardous drinking statuses at follow-ups as well as obtain parallel measures for drug use. Predictions are based on the parent R01 findings suggesting (but not demonstrating) a dose-dependent positive relationship for de-coupling therapy elements but not anxiety reduction therapy elements in terms of alcohol outcomes; i.e., CBT-DC > CBT-O > CBT-AR on alcohol outcomes. As a means of confirming that the therapeutic mechanisms targeted were responsible for the group differences obtained, process measures of the therapeutic mechanisms are included at all assessments both to verify their dose-dependent activation in groups and to track temporal patterns of change on the mechanisms relative to the outcomes over follow-ups

Project Timeline (Table 1):

Months	Activities
1 to 3	1) hire staff; 2) purchase equipment/supplies; 3) create study documents and database; 4) therapist and interviewer training.
4 to 12	1) recruit 65 participants; 2) begin follow-up data collection; 3) begin data entry; 4) quarterly DSMB reports.
13 to 24	1) recruit 95 participants; 2) follow-ups continues; 3) continue data entry; 4) quarterly DSMB reports
25 to 36	1) recruit 95 participants; 2) follow-ups continues; 3) continue data entry; 4) quarterly DSMB reports
37 to 48	1) recruit 95 participants; 2) follow-ups continues; 3) continue data entry; 4) quarterly DSMB reports
49 to 54	1) recruitment complete follow-up data collection only; 2) clean data; 3) break blind; 4) begin data analysis
55 to 60	1) complete data analysis; 2) manuscript preparation and submission

1.0 INTRODUCTION AND OVERVIEW

While it has long been observed that negative affectivity is strongly related to excessive alcohol use (Babor, 1996), it was not until the emergence of modern diagnostic criteria that the size of this association could be quantified using some standard metric. In clinical samples, about 50% of AUD treatment patients can be diagnosed with a co-occurring anxiety disorder (Kushner et al., 2005; Kushner et al., 1990). Numerous community-based epidemiological samples show that alcohol dependence is two to four times more common among individuals with anxiety disorders (Grant et al., 2004; Kessler et al., 1997; Regier et al., 1990). Because anxiety disorders and AUDs are among the most common psychiatric conditions (about 15% and 12% of adults, respectively), the increased risk

for AUDs associated with co-occurring anxiety disorders includes a very large absolute number of individuals. The purpose of this study is to establish a brief CBT intervention that can largely, if not fully eliminate the deleterious effect of common co-occurring anxiety disorders on AUD treatment outcomes

2.0 RESEARCH OBJECTIVES

As noted earlier, this is a continuation study from the parent project showing that a cognitive-behavioral therapy (CBT) we designed to augment standard alcohol use disorder (AUD) treatment for patients with co-occurring anxiety disorder can improve the short-term (i.e., 4 month) alcohol outcomes of these patients compared to those receiving standard AUD treatment with a robust control group (relaxation training) in a randomized controlled trial. The CBT treatment in the parent study divided its focus equally between the goals of anxiety reduction (3 sessions) and decoupling anxiety and alcohol use/urges (3 sessions). However, because both the relaxation control group and the CBT group experienced roughly the same (not significantly different) degrees of anxiety reduction, we deduced that the added clinical benefit came from the decoupling focus of the CBT therapy, which was not present in the control group. This conclusion, along with the modest effect sizes obtained, motivated us to determine two additional pieces of information: 1) could increasing the de-coupling emphasis of the CBT beyond three sessions (i.e., increased dose) provide additional therapeutic benefits; and, 2) is the therapeutic value of the de-coupling elements only realized when combined with a purely anxiety reduction focus. The present study was design to answer these questions by dismantling the two both therapy foci into separate therapy groups (allowing for increased dose of each and an unambiguous evaluation of each foci on its own) and comparing these to the original CBT therapy that combined the therapy foci.

2.1 Primary Aim: To test the dismantled CBT effects by comparing the CBT-Decoupling (DC) group to the CBT-Anxiety Reduction (AR) group on alcohol outcomes. We predict that the CBT-DC group will have superior alcohol outcomes compared to the CBT-AR group. This result would confirm that the de-coupling therapy elements are more active in improving AUD outcomes than are the anxiety reduction therapy elements.

2.2 Secondary Aim: To test dose vs. synergy effects of de-coupling therapy by comparing the CBT-DC group to the CBT-Original (O) group on alcohol outcomes. We predict that the CBT-DC group will have superior alcohol outcomes compared to the CBT-O group. This result would show the dose-response effects of de-coupling therapy on alcohol outcomes (6 vs. 3 DC sessions) and confirm that the de-coupling therapy effect on alcohol outcomes is not dependent upon its combination (synergy) with anxiety reduction elements. Alternatively, if CBT-O is superior to CBT-DC, then the critical role of synergy would be demonstrated.

2.3 Tertiary Aim: To test the dose effects of anxiety reduction therapy by comparing the CBT-AR group to the CBT-O group on alcohol outcomes. We predict that the CBT-O group will have superior alcohol outcomes compared to the CBT-AR group. Assuming synergy was ruled out in the Secondary Aim, this result would further confirm the hypothesized dose-response effects of de-coupling therapy on alcohol outcomes (3 vs. zero DC sessions). Alternatively, if the CBT-AR group is superior to the

CBT-O group, then a critical role for the higher dose of anxiety reduction therapy would be demonstrated.

2.4 Mechanism Manipulation Checks: Compare groups on pre- to post-treatment change in mechanism process measures. Determining that the interventions affected the targeted mechanism in the dose-dependent manner intended (e.g., reduction in AR-AOEs is greatest in the CBT-DC group) will allow group differences obtained to be attributed to the action of the targeted mechanisms.

2.5 Time-Dependent Effects: Explore time-dependent effects between mechanism process measures and alcohol outcomes from BL through 1-mo, 4-mo, and 8-mo FU assessments. These results will allow for causal inferences between mechanisms and outcomes by demonstrating temporal priority in change.

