6.5. The CBT Therapy (six daily one-hour sessions)

6.5.1. Background of the CBT and modifications pertinent the proposed work. The CBT treatment used in the parent R01 (see Kushner et al., 2013) included three 1-hour anxiety reduction sessions (AR content set) and three 1-hour alcohol-anxiety de-coupling sessions (DC content set). Parallel clinical domains are addressed in both the AR and DC content sets focused on: 1) cognitive restructuring; 2) coping skills training; and, 3) practice with exposure/habitation. The material for the AR content set was synthesized from a survey of published work related to the bio-psycho-social model of anxiety (e.g., Barlow, 2001; Barlow et al., 1989), cognitive restructuring of anxiety related cognitions (e.g., Beck, 1976; Beck et al., 2005; Ellis & Harper, 1975), breathing retraining for coping with anxiety (e.g., Han et al., 1996), and exposure for habituating conditioned anxiety responses (e.g., Foa & Kozak, 1986). The material for the DC content set was synthesized from published work related to the vicious cycle model of alcohol and anxiety (e.g., Kushner et al., 2000a), cognitive restructuring of alcohol-related beliefs and expectancies (e.g., Beck et al. 1993, Kushner et al., 2000b), alternatives to drinking for coping with anxiety (e.g., Larimer et al., 1999), and exposure for habituating conditioned associations between anxiety and alcohol cues (e.g., Cooney et al., 1997; Litt et al., 1990; Sinha, 2009). The therapy doses chosen in the parent R01 (3 sessions for anxiety reduction and 3 for alcohol-anxiety de-coupling for 6 total sessions) represented a balancing of

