competing interests in delivering therapeutic levels of the interventions for both theoretically central mechanisms (anxiety reduction and anxiety-alcohol de-coupling) while: 1) not interfering with the full day of standard AUD programming; 2) beginning at least one week after detoxification to accommodate recruitment time and to ensure therapy is delivered post-acute detoxification; and, 3) concluding treatment prior to discharge from the 28-day residential AUD program to avoid conflicts with re-location, return to place of employment, transportation etc. These parameters will apply to the renewal project conducted in the same institutional setting as the parent R01. The CBT-O group in the renewal work will be the same CBT protocol used in the parent R01; i.e., the three-session AR content set plus the three-session DC content set for a total of six sessions. The two dismantled CBT therapy conditions will include one of the three-session content sets (AR or DC) plus one additional session devoted to each of the three clinical domains (cognitive restructuring, coping skills, and exposure/habituation) within that set for a total of six sessions for all therapy groups.

6.5.2. Elements common to all three CBT therapy group conditions:

a) Psycho-Education in which the participant is introduced to the basics of the CBT model of therapy. This portion of the treatment is largely didactic and includes powerpoint slides that are narrated by the therapist.

b) Cognitive Coping Skills in which the participant is taught how to distinguish between thoughts, feelings and situations that are associated with negative affect (i.e., stress, anxiety and depression) and how each of these components interact with the others. Participants are then taught and practice a standard CBT skill referred to as "cognitive-restructuring" in which thoughts and beliefs that aggravate negative affect through their inaccuracy, incompleteness, or exaggeration are systematically examined and modified to better align with probabilistic reality and logical inference. This process has been shown in 100s of separate studies to improve anxiety and depression symptoms in psychiatric patients.

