c) Behavioral Coping Skills in which the participant is taught behavioral strategies to reduce negative affect and tension. These include slow-paced diaphragmatic breathing and "behavioral activation." Behavioral activation is an intervention in which goals identified as important by the participant in several domains of life (e.g., social, health, occupational, educational) are identified and a specific realistic plan of activities aimed at moving toward those goals is developed. Past studies in psychiatric patients have shown that engaging in behavioral activation relieves negative affect and improves life satisfaction.

d) Coping Skills Practice with Guided Imagery exposure in which participants will have the opportunity to apply cognitive and behavioral coping skills while imagining being in a common situation in which they have experienced moderate negative affect associated with their anxiety disorder. The actual content of the guided imagery exercise is provided by the participant with explicit instructions and therapist guidance aimed at avoiding content related to extreme distress such as that associated with trauma. Using guided imagery "exposure" in this way is a standard component of CBT used when real life (in-vivo) exposures are too intense or are not feasible; as will generally be the case while residing at Fairview hospital during the course of the CBT. It is generally found that imagery based exposures of this sort are less intense than actually being in the situation imagined. Also, it is a central tenet of CBT that therapeutic skills that are practiced while being in stressful situations (or imagining them in this case) are more clinically effective; i.e., are more likely to be deployed at all or to be deployed effectively when real-life stressors occur. The PI is a licensed

psychologist and practicing CBT therapist who has routinely used this and other CBT techniques described for over 20 years.

e) Post therapy session knowledge quizzes will be given after each session to document that the participant understood the major points covered in that session. These quizzes are designed to be easy to answer correctly if the patient was actively participating in the session. The therapist will provide immediate feedback on the quiz and will emphasize why another answer is considered correct if any questions are answered incorrectly.

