f) Between session practice and monitoring will be assigned following each of the six CBT therapy sessions that will focus on practicing the skill taught in the session and keeping a simple record of their anxiety level and urge to use alcohol between the sessions as well as whether they were able to effectively use the therapy skill to reduce the negative affect/urge.

6.5.2. Elements distinguishing the three randomized CBT therapy group conditions:

a) CBT-Anxiety Reduction Condition: Those assigned to this group will undergo all of the CBT elements outlined above but with all six sessions focused on negative affect without specific reference to alcohol alcohol use.

b) CBT Anxiety-Alcohol Interaction Condition: Those assigned to this group will undergo all of the CBT elements outlined above but with all six sessions focused on the interaction of negative affect with alcohol use/urges.

c) CBT Combination Condition: Those assigned to this group will undergo all of the CBT elements outlined above but with three of the six sessions focused exclusively on reducing negative affect without reference to alcohol use and the other three sessions focused exclusively on the interaction of negative affect with alcohol use/urges.

6.5.3. Therapist training. The study PI is primarily responsible for training and supervision of study therapists. The training sequence established in the parent R01 will also be used in the renewal work including: 1) reading the therapist and patient treatment manuals; 2) observing training tapes that have been prepared for that purpose; 3) observing the trainer administer the treatment; and 4) being observed and critiqued by the trainer while delivering the treatment. Our experience suggests that delivery of the therapy via the structured PowerPoint slideshow (above) ensures a uniform delivery of the basic content of the therapy, even with newly trained therapists. Supervision with the PI takes place on a weekly basis throughout the treatment phase of the project (separately for each therapist) in which the progress of each case is discussed and any treatment issues are resolved.

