7.6. Secondary Aim: To compare the CBT-DC and CBT-O groups on alcohol outcomes

The importance of this comparison includes confirming our hypothesis that 6 DC sessions are superior to 3 DC sessions in terms of alcohol outcomes (DC dose: high vs. low) while also ruling out the alternative hypothesis that, contrary to study predictions, de-coupling therapy elements can only exert a therapeutic effect on alcohol outcomes when combined with anxiety reduction elements ("synergy"). Regarding the affirmative dose prediction, we can estimate the effect of the CBT-O group to be the same as that of the CBT in the parent R01 (i.e., 41% relapse at 4 months), while keeping all other parameters, including the CBT-DC group effect estimate of 21% relapse, the same as outlined for the Primary Aim. These estimated results would represent a medium effect ($OR = 2.6$), which would require a sample of 94 per group to identify with 80% power an effect with $\alpha = 0.05$. (Again, we anticipate continuous/count tests will have greater power than categorical tests.) If, however, contrary to our study predictions, synergy between the therapy components is necessary,

then we would expect CBT-DC to resemble TAU only in outcome (61% relapse) with the CBT-O result still being the same as in the parent R01 (again, 41% relapse). This would provide roughly the same power to detect the unexpected synergy effect as there will be to detect the predicted dose effect; albeit, with opposite directional effects.

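### A CBT-DC win over CBT-O would show that sessions devoted solely to anxiety reduction are unnecessary, not that de-coupling works without any anxiety-reduction technique

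*Combined protocol and SAP*

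**What the plan says.** The Secondary Aim (Study Aims and Section 2.2) compares CBT-DC with CBT-O. A CBT-DC win is said to show a dose effect and also to "confirm that the de-coupling therapy effect on alcohol outcomes is not dependent upon its combination (synergy) with anxiety reduction elements". Section 7.6 says the comparison rules out the alternative that "de-coupling therapy elements can only exert a therapeutic effect on alcohol outcomes when combined with anxiety reduction elements". Section 2.0 describes the dismantled arms as "allowing for increased dose of each and an unambiguous evaluation of each foci on its own". Section 2.3 makes its reading of CBT-O versus CBT-AR conditional on synergy having been excluded in this way.

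Three places describe what the arms contain:

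- Section 6.5.1 puts "breathing retraining for coping with anxiety", restructuring of anxiety-related thoughts, and anxiety exposure in the AR set. It says each dismantled arm is built from one content set, AR or DC, with one further session in each clinical domain of that set.
- The first Section 6.5.2 lists elements common to all three arms. Among them is cognitive restructuring of thoughts that aggravate negative affect, of which it says "This process has been shown in 100s of separate studies to improve anxiety and depression symptoms in psychiatric patients". The behavioral coping element teaches ways to lower negative affect and tension: "These include slow-paced diaphragmatic breathing and" behavioral activation.
- The second Section 6.5.2 says of the CBT-DC arm: "Those assigned to this group will undergo all of the CBT elements outlined above but with all six sessions focused on the interaction". The interaction meant is the one between negative affect and drinking or urges to drink.

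For power, Section 7.6 says that if synergy is necessary "we would expect CBT-DC to resemble TAU only in outcome (61% relapse", against 41% in CBT-O, and that power would be about equal to that for the dose effect. Section 7.7 adds that in this comparison dose and synergy should act in opposite directions.

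**The concern.** The synergy inference needs an arm that receives de-coupling without anxiety-reduction elements. As Section 6.5.2 describes it, CBT-DC is not such an arm: it includes at least one technique that the plan itself assigns to the AR set, and another that overlaps with that set.

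Suppose de-coupling works only alongside some anxiety-coping skill, and the shared techniques provide that skill. CBT-DC then has six de-coupling sessions plus the enabling skill, and CBT-O has three plus the skill. CBT-DC could win although synergy is real, and the plan would report synergy as excluded. Section 2.3 would carry that error into the Tertiary Aim.

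**Working it through.** **Contents compared.**

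- Breathing: in the AR set under 6.5.1, and common to all arms under the first 6.5.2. This is a direct mismatch.
- Cognitive restructuring: 6.5.1 has anxiety-related thoughts in the AR set and alcohol beliefs and expectancies in the DC set. The shared element in 6.5.2 is defined by negative affect (stress, anxiety, depression), so it overlaps with the AR version.
- Behavioral activation: shared under 6.5.2, but not named in the AR set of 6.5.1. It does not count as AR content.
- Imagery: shared under 6.5.2 as practice of coping skills. The AR exposure in 6.5.1 serves habituation. The overlap is arguable, and the point does not need it.

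**The plan's own figure.** Inputs from 7.6: 41% (CBT-O), 21% (CBT-DC), alpha 0.05, power 80%. The test is two-sided, as stated in 7.5. With p̄ the mean of p1 and p2, and d = |p1 − p2|:

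n = [1.96·√(2p̄(1−p̄)) + 0.8416·√(p1(1−p1)+p2(1−p2))]² / d²

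= [1.96·√0.4278 + 0.8416·√0.4078]² / 0.20² = 82.75, so 83 per group.

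The continuity correction, (n/4)·[1+√(1+4/(n·d))]², gives 92.5, so 93 per group. The plan states 94, so its figure is reproduced within rounding. The odds ratio is (0.41/0.59)/(0.21/0.79) = 2.61, against 2.6 stated.

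**Power of the synergy scenario.** With n = 100 per group (7.8), two-sided 0.05, uncorrected:

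power = Φ{[d√n − 1.96·√(2p̄(1−p̄))] / √(p1(1−p1)+p2(1−p2))}

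- Dose effect, 41% vs 21%: (2.000 − 1.282)/0.639 = 1.12, power 0.87.
- Synergy as planned, 61% vs 41%: (2.000 − 1.386)/0.693 = 0.89, power 0.81.

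These are near enough to the plan's claim of similar power, provided that CBT-DC falls all the way to the treatment-as-usual (TAU) rate of 61%.

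**If the shared techniques supply part of the benefit.** The full synergy benefit is 61 − 41 = 20 percentage points. The share supplied is an assumption; the documents give no value.

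| Share supplied (assumed) | CBT-DC relapse | Power vs 41% |
|---|---|---|
| 0 | 61% | 0.81 |
| 1/4 | 56% | 0.57 |
| 8/20 | 53% | 0.40 |
| 1/2 | 51% | 0.29 |

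The 53% row uses the parent trial's relaxation-training relapse rate purely as an illustration. It is not an estimate for CBT-DC. If the share is complete, synergy leaves no deficit in CBT-DC. The larger de-coupling dose could then take CBT-DC below 41%, so the two effects would not oppose each other as 7.7 assumes.

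These figures concern the power to see a CBT-O advantage. They do not give the probability that a CBT-DC win would be misread; that part of the point is logical.

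**The case against.** The best defense is that the arms are separated by focus, not by technique. Section 6.5.1 says openly that both content sets cover the same three clinical domains, and the second 6.5.2 separates the arms by what the sessions address. Section 2.0 frames the synergy question as whether de-coupling needs to be combined with a focus solely on anxiety reduction. CBT-DC has no such sessions, so a win answers that question. Preferring the CBT-DC package as delivered would also be valid, because its coping skills come with it.

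All of this stands, and it limits the point. A reader might infer that CBT-DC is simply another combined treatment and that the Secondary Aim says nothing about synergy. The documents do not support that reading, because the contrast does test dedicated AR sessions. What remains is that the Study Aims, 2.2 and 7.6 state the conclusion for anxiety-reduction elements in general, which is wider than the contrast supports.

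Two existing safeguards help but do not close the gap. The manipulation checks (2.4, 7.8) compare change between groups, and a larger anxiety reduction in CBT-AR would not show that CBT-DC had none. The fidelity review (6.5.4) covers proscribed content and contamination across arms, but it cannot classify breathing consistently while 6.5.1 and 6.5.2 differ. The plan does not tie the synergy conclusion to either safeguard.

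A reader might also want synergy declared excluded only if anxiety change in CBT-DC is negligible. That would be unsound. All arms receive residential TAU and there is no randomized TAU-only arm, so change within an arm cannot be attributed to the shared techniques.

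**Conclusion.** The concern holds in a limited form. A CBT-DC win over CBT-O would support the claim that dedicated sessions aimed only at anxiety reduction are not needed beyond the techniques shared by all arms. It would not establish that de-coupling works without any anxiety-reduction technique. The reading of the Tertiary Aim in 2.3 inherits the same limit.

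The power of about 0.81 for the synergy scenario is a best case. It falls to about 0.40 at an assumed 53%, and lies between 0.57 and 0.29 for assumed shares of a quarter to a half. The 94 per group for the dose effect is not in question.

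The verdict assumes that 6.5.2 describes CBT-DC as delivered; the treatment manuals are not in the documents. If 6.5.1 governs and CBT-DC holds only the DC set, the point weakens but does not vanish, because that set includes ways other than drinking to cope with anxiety.

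**What to change.** 1. Reconcile 6.5.1 with the two sections numbered 6.5.2 on which techniques are specific to the AR set and which are shared, and align the fidelity checklist with the result.
2. In the Study Aims, 2.2 and 7.6, restate the conclusion as concerning dedicated AR-focused sessions beyond the techniques common to all arms. Reword the condition in 2.3 (and its copy in the Study Aims) to match, and make the opposite-direction remark in 7.7 conditional.
3. In 7.6, keep the 61% versus 41% scenario and its statement of similar power, but label both as a best case that assumes the shared techniques supply none of the synergy benefit.
4. Report baseline-to-post-treatment anxiety change within CBT-DC beside the Secondary Aim result, as a qualifier and not as a pass/fail condition.

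These are wording changes plus one descriptive report from measures already collected, with no effect on sample size. The cost is a narrower Secondary Aim claim.
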